2.3. Benefit/Risk Assessment

Sisunatovir is not expected to provide any clinical benefit to healthy participants. This study is designed primarily to generate safety, tolerability, and PK data for further clinical development.

For healthy participants participating in this study, no clinical benefit is expected. The purpose of the study is to provide the basis for further clinical development of sisunatovir as a potential new, pharmacological agent for the treatment of RSV LRTI.

As of 14 September 2022, no specific human risks have been identified; postulated risks based on nonclinical studies are summarized in [Section 2.2.3](#). The clinical impact of these potential risks will be minimized through standard, intensive, inpatient monitoring of the participants following administration of multiple oral doses of the study intervention.

More detailed information about the known and expected benefits and risks and reasonably expected AEs of sisunatovir may be found in the IB, which is the SRSD for this study. Refer to the Study Intervention(s) table in [Section 6.1](#) for a complete description of SRSDs.,

2.3.1. Risk Assessment

Potential Risk of Clinical Significance	Summary of Data/Rationale for Risk	Mitigation Strategy
Study Intervention PF-07923568		
Hepatobiliary system effects	
Degenerative and inflammatory changes in the bile duct of both rats (≥ 60 mg/kg/day) and dogs (≥ 45 mg/kg/day) in studies of up to 28 days, with elevated plasma levels of ALP, ALT, and GGT in dogs only. Evidence of recovery for all findings following a 14-day treatment-free period.
 
To date, mild transient elevations of liver enzymes have been observed in a few participants within clinical studies.
	Standard monitoring including laboratory (ie, transaminases, ALP, GGT) and AE monitoring.
Gastrointestinal effects	
Transient dose-related incidence of emesis and liquid feces in dogs at doses ≥ 15 mg/kg/day in studies up to 28 days. Additionally, inflammation in the duodenum, gall bladder, and liver at 45 mg/kg/day noted in 28-day dog study.
 
In completed adult clinical studies sisunatovir has been associated with mild GI AEs.
	As this is an investigational agent, there is some risk that is mitigated by close observation of AEs, etc. Participants will be closely evaluated in an inpatient setting to monitor for GI AEs. If needed, palliative alleviating measures such as antiemetics may be provided.

Potential Risk of Clinical Significance	Summary of Data/Rationale for Risk	Mitigation Strategy
Cardiovascular effects	
Myocardial degeneration and necrosis were noted at 240 mg/kg/day (non-tolerated dose) in a 14-day rat study.
 
No similar effect in rats at 120 mg/kg/day in the 28-day study, or in dogs at any dose, for 14 or 28 days.
 
To date, Phase 1 studies in healthy participants and a Phase 1b study in pediatric participants has not shown clinically significant changes in safety laboratory parameters (including troponin in C5241001), ECGs and vital signs related to Sisunatovir.
	Monitoring will include VS, including heart rate and ECG assessments.
Other		
Risk of COVID-19 exposure during study	During the pandemic, study participants could be exposed to the SARS-CoV-2 virus during study participation. This could lead to increased health risk for this participant and others in the study.	Assessment of risk for, symptoms of, or testing for COVID-19 may be performed at screening, admission to the CRU, and/or at other times during the study at investigator discretion and according to local site policies.

2.3.2. Benefit Assessment

For healthy participants participating in this study, no clinical benefit is expected.

2.3.3. Overall Benefit/Risk Conclusion

This study is designed primarily to generate PK, safety, and tolerability data in Chinese individuals.

Taking into account the measures to minimize risk to study participants, the potential risks identified in association with sisunatovir are justified by the broader potential benefits to patients with RSV, if further development of sisunatovir is successful.

3. OBJECTIVES AND ENDPOINTS

Objectives	Endpoints
Primary:	Primary:

To evaluate the PK of sisunatovir after single dose and multiple doses in Chinese healthy participants	Sisunatovir plasma exposure for single and multiple doses: 
Post dose on Day 1: C_{max}, AUC_{last}, AUC_{tau} ($\tau=12$), and AUC_{inf} as data permit.Post first dose on Day 4: C_{max}, AUC_{tau}Post dose on Day 8: C_{max}, AUC_{tau}
Secondary:	Secondary:

To further characterize the PK profile of sisunatovir after single dose and multiple doses of sisunatovir in Chinese healthy participants	Additional sisunatovir plasma PK parameters: 
Post dose on Day 1: T_{max}, $t_{1/2}$, MRT, V_z/F, and CL/F as data permitPost first dose on Day 4: T_{max}Post dose on Day 8: T_{max}, $t_{1/2}$, accumulation ratio on AUC_{tau} (R_{ac}) and on C_{max} ($R_{ac,Cmax}$), MRT, V_z/F, CL/F, C_{trough}, C_{av}, AUC_{last}, AUC_{inf} and PTR as data permit

To evaluate the safety and tolerability of sisunatovir following single and multiple dose in Chinese healthy participants	
AEs/SAEs, clinical safety laboratory tests, vital signs, 12-lead ECGs
Tertiary/Exploratory:	Tertiary/Exploratory:
CCI	

To explore PK of sisunatovir by microsampling technique, if feasible	
Concentration of sisunatovir from paired samples obtained via microsampling compared to plasma sampling (if possible)

4. STUDY DESIGN

4.1. Overall Design

This is a Phase 1, single-center, open-label and single-arm study to investigate PK, safety and tolerability of 200 mg sisunatovir given as a single dose on Day 1 in a fasted state followed by repeated twice daily doses (200 mg BID, Q12 hours) from Days 4-7 plus 1 morning dose on Day 8 in a fed state in Chinese healthy participants. Approximately 12 participants in total will be included in this study. If a participant discontinues before completing the study, or withdraws for reasons unrelated to the safety of the treatment, the participant may be replaced at the discretion of the investigator upon consultation with the sponsor.

A summary of the schedule of study participation and procedures is provided (see [Schedule of Activities](#)). The study will consist of a Screening visit, a Treatment period of single dosing (Day -1 to Day 3) and multiple dosing (Day 4 to Day 11), and a Follow-up contact. The total duration of participation from the Screening visit to the Follow-up contact will be up to approximately 71 days.

The study period will begin with informed consent from the first participant and will end with the follow up examination of the last participant.

Informed consent to participate in the study will be obtained before initiation of any trial-related activities. Screening examination will be conducted within 28 days before the first study drug administration. Participants will be admitted to the CRU on Day -1, 1 day before the first study drug administration. On Day 1 after fasting for at least 10 hours, all participants will receive a single oral dose of sisunatovir 200 mg at approximately 8:00 am \pm 2 hours in the morning. The participants will be maintained in a fasted state for 4 hours after dosing and undergo serial PK blood sampling for 72 hours post-dose. On Days 4 to 7, participants will receive oral dose of sisunatovir 200 mg twice daily (Q12 hours) in a fed state. On Day 8, the dosing of sisunatovir will be administered under fed condition at approximately 8:00 am \pm 2 hours in the morning. Participants may be discharged on Day 11 after all study procedures are completed.

A follow up contact will be completed at least 28 calendar days and up to 35 calendar days after the last dose of investigational product to capture any potential AEs and concomitant treatments, and to confirm appropriate contraception usage. This follow-up assessment may be conducted via telephone.

4.2. Scientific Rationale for Study Design

The primary purpose of this study is to characterize the PK of sisunatovir in healthy Chinese adult participants. The selected dose in this study was well tolerated in previous clinical studies and therefore placebo control to evaluate safety is not needed. Males and females are to be recruited in the study.

Single- and multiple-dose periods are included in this study to allow characterization of the PK of sisunatovir following single dose and multiple doses in healthy Chinese participants. Repeated dosing for 5 days is sufficient for sisunatovir to reach its steady state, based on previous PK data and will permit comparison to PK data in Japanese and Westerners from Study C5241001, C5241005 and C5241006 which collected steady-state data on Day 5. Blood sampling up to 72 hours post-dose is adequate for the characterization of the elimination phase for sisunatovir considering its half-life of 7-10 hours.

Sisunatovir single dose on Day 1 will be administered without food in order to directly compare PK among Chinese, Japanese and Westerners. While given as repeated twice daily doses (Q12 hours) from Days 4-7 plus 1 morning dose on Day 8, sisunatovir will be given with food (typical Chinese breakfast, not high-fat high calorie) to mimic future clinical practice. Data obtained from such a design could also be helpful to preliminarily evaluate typical Chinese breakfast effect on the PK of sisunatovir.

If feasible, exploratory micro-sampling PK samples for the measurement of sisunatovir concentrations will be collected, in order to evaluate micro-sampling approach using the Tasso[®] device.

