2.2.4. Clinical Overview

To date, 5 clinical studies of sisunatovir have been completed; each study was conducted in healthy adults. Key design features of the completed clinical studies are provided in [Table 3](#), and summaries of the key clinical pharmacology, clinical efficacy and clinical safety data from the completed studies are provided in the sections below.

Table 3. Completed Sisunatovir Studies

Study Number (Status)	Study Type/Key Design Features	Study Population	Dose, Dosing Regimen	Formulation Used
C5241001 (previously REVC001) (completed)	Phase 1, randomized, double-blind, placebo-controlled, SAD and MAD study to evaluate the safety, tolerability, PK, and food and formulation effect	Healthy participants Part A (SAD): 24 Caucasian and 12 Japanese	Part A: 10, 30, 60, 175, 250, 350, or 525 mg single dose	DIC ^a
		Part B (MAD): 24 healthy participants	Part B: 175, 250, or 350 mg BID x 5 days for a total of 9 doses	DIC ^a
		Part C (food effect and formulation): 16 healthy participants	Part C: 200 mg single dose	DIC ^a Liquid Formulation ^a
C5241002- previously REVC002 (completed)	Phase 2a, randomized, double-blind, placebo-controlled	Healthy participants inoculated with RSV Challenge Virus (CV) 66 participants	200 mg or 350 mg BID for a total 10 doses;	DIC
C5241003 Previously REVC003 (completed)	Phase 2, randomized, double-blind, placebo-controlled study to investigate PK, safety, and tolerability	Hospitalized pediatric patients with RSV lower respiratory tract infection (LRTI): Part A – 19 Part B – 32	Part A: single dose (2.5 mg/kg for participants 6-36 months, inclusive; and 2 mg/kg for participants \geq 1 month to <6 months of age) Part B: multiple doses (2.5 mg/kg in 1-<6 months and up to 5 mg/kg in 6-36 months) q12h for 5 days	DPB
C5241004- previously REVC004 (completed)	Phase 1, adaptive, part-randomized, part open-label study to evaluate drug interactions, safety and tolerability	Healthy participants; 82	200 mg; BID;	DIC
C5241005- previously REVC005 (completed)	Phase 1, open-label, single-dose, study to evaluate the PK, safety, and tolerability	Healthy participants; 9	200 mg, 4 single doses total; 1 ×: DIC (fed) 1 ×: DPB dispersed in H ₂ O (fed) 1 ×: DPB dispersed in H ₂ O (fasted) [wash-out: 3 days between each of the 3 dosing days]	DIC DPB

Table 3. Completed Sisunatovir Studies

Study Number (Status)	Study Type/Key Design Features	Study Population	Dose, Dosing Regimen	Formulation Used

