4.3. Justification for Dose

The study dose and duration were selected based on the safety, tolerability and PK results in previous studies and the proposed clinical dose for future studies. The dose level of 200 mg BID is current proposed dose level for the following clinical development in adults. This dose was also studied in healthy participant studies C5241001, C5241005 and C5241006, which would allow the comparison of safety and PK among Westerner, Japanese and Chinese.

The single dose up to 525 mg for sisunatovir and multiple doses up to 350 mg BID × 5 days for a total dose of 9 doses were studied in Phase 1 study (C5241001), while a higher dose of 400 mg BID × 5 days was studied in C5241006. Up to a single dose of 525 mg or multiple doses of 400 mg BID, sisunatovir was generally safe and well-tolerated in all healthy participants.

The effect of food on the PK of sisunatovir has been variable in Phase 1 studies. However, the effect of food on the PK of sisunatovir using the formulation to be used in this study (dry powder blend in capsules) showed minimal food effect. Therefore, the concern of unacceptable safety and tolerability due to potentially higher exposure caused by food effect is not expected in Chinese healthy participants with administration of repeated twice daily doses (Q12 hours) of sisunatovir.

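### Do Sections 4.2 and 4.3 claim comparator data that Table 3 does not show, and does the plan need to change for it?

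*Protocol*

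**What the plan says.** Protocol Section 4.2 makes two statements about comparison across populations. On the multiple-dose period, it says that five days of dosing "will permit comparison to PK data in Japanese and Westerners from Study C5241001, C5241005 and C5241006 which collected steady-state data on Day 5". On the single-dose period: "Sisunatovir single dose on Day 1 will be administered without food in order to directly compare PK among Chinese, Japanese and Westerners". It then gives a second use for the design, which "could also be helpful to preliminarily evaluate typical Chinese breakfast effect on the PK of sisunatovir".

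Section 4.3 justifies the dose: "The dose level of 200 mg BID is current proposed dose level for the following clinical development in adults". The next sentence reads: "This dose was also studied in healthy participant studies C5241001, C5241005 and C5241006", and says this allows Western, Japanese and Chinese data to be compared. A little later it adds "while a higher dose of 400 mg BID × 5 days was studied in C5241006".

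Table 3 in Section 2.2.4 describes C5241005 as a "Phase 1, open-label, single-dose, study to evaluate the PK, safety, and tolerability", with the regimen "200 mg, 4 single doses total" and a 3-day wash-out. For C5241001 it lists:

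- Part A: single doses of 10, 30, 60, 175, 250, 350 or 525 mg, in 24 Caucasian and 12 Japanese participants.
- Part B: twice-daily dosing for 5 days at 175, 250 or 350 mg, in 24 participants.
- Part C: single doses of 200 mg, in 16 participants.

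C5241006 is not in Table 3. The text below the table calls it an ongoing multiple-dose study at one Belgian site and gives neither dose levels nor ethnic group.

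**The concern.** A reader of Sections 4.2 and 4.3 would expect three earlier studies to supply Day 5 steady-state data at 200 mg twice daily, Japanese participants included. Table 3 does not bear this out. C5241005 gave isolated single doses. C5241001 gave twice-daily dosing only at other levels. The only Japanese participants listed had single doses at levels other than 200 mg. Section 2.2.4 also reports that exposure rises more than in proportion to dose, so results at 175 or 250 mg cannot simply be scaled to 200 mg.

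The fasted Day 1 dose is justified mainly by the comparison between populations, and the study is meant to support registration in China. If the comparators were not there, the design would rest in part on a claim that could not be met.

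**Working it through.** There is no power, alpha or sample-size figure to reproduce. The check sets the passages side by side, with a few sums.

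**Are the C5241001 rows of Table 3 intact?** Participants by part: 24 + 12 + 24 + 16 = 76. The table footnote gives 8 on the liquid form and 68 on capsules: 8 + 68 = 76. They agree, so no part seems to have been lost.

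**Can C5241005 be at steady state?** Inputs: half-life 7 to 10 h (Section 2.2.4), wash-out 3 days = 72 h (Table 3). Assuming one-compartment decline, the fraction left is 2^(−72/t½).

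- t½ = 7 h: 2^(−72/7) = 0.0008, or 0.08%.
- t½ = 10 h: 2^(−72/10) = 0.0068, or 0.68%.

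Predicted accumulation, 1/(1 − 2^(−τ/t½)), is 1.001 to 1.007 for τ = 72 h, against 1.44 to 1.77 for τ = 12 h. Section 2.2.4 reports 2- to 4-fold on repeated dosing. C5241005 therefore holds single-dose data only.

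**Does C5241001 Part B match this study?** The schedule does: this study gives 4 × 2 + 1 = 9 doses over Days 4 to 8, and Part B also gave 9. The dose does not: 175/200 = 0.875, 250/200 = 1.25 and 350/200 = 1.75. The Part B levels bracket 200 mg without including it.

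**What Sections 4.2 and 4.3 need, against what is documented:**

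| Named study | Day 5 steady state | 200 mg | Japanese participants |
|---|---|---|---|
| C5241001 | Part B, at 175, 250, 350 mg | Part C, single dose, 16 participants | 12 in Part A; Parts B and C not stated |
| C5241005 | No | Yes, single doses | Not stated |
| C5241006 | Yes, on Section 4.2 | Yes, on Section 4.3; nothing contradicts it | Not stated |

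**How firm is each conflict?**

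1. The steady-state clause in Section 4.2 conflicts with Table 3 if it governs all three studies. Grammatically it can attach to C5241006 alone.
2. In Section 4.3 the preceding sentence speaks of a dose level. If the 200 mg amount is meant, C5241001 Part C and C5241005 both fit. If 200 mg twice daily is meant, neither does.
3. The Day 1 sentence in Section 4.2 does not claim a matching dose, so Japanese single-dose data at other levels do not contradict it. Only Section 4.3 ties the comparison to a dose.
4. The Japanese gap is an absence of listing. Table 3 gives key design features, and Section 2.2.4 refers the reader to the Investigator's Brochure for detail.

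**Does anything in the plan use the comparison?** The visible objectives and endpoints (protocol Section 3, SAP Section 2.2) concern PK and safety in this study's participants. Protocol Section 9.1 and SAP Section 5.1 state that there is no hypothesis. SAP Sections 6.1 and 6.2 summarise parameters and concentrations by study day, and no visible SAP analysis brings in data from another study. Protocol Section 9.5 bases the 12 participants on a Chinese regulatory requirement.

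**The case for a change.** The best case for acting is this. The subject of the sentence in Section 4.2 is repeated dosing, so naming a single-dose study there is wrong on any parsing. Section 4.3 then names the same three studies straight after 200 mg twice daily. Even on the kindest reading of both, no Japanese data at 200 mg or at steady state are documented. Table 3 does show 200 mg twice daily in C5241002 and C5241004, yet neither is named as a comparator. Rewording would cost a few sentences.

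Two parts of this stand. C5241005 does not belong in a list of steady-state sources, and the origin of a Japanese comparator at 200 mg is not shown.

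The rest is weaker. That the comparison is truly narrower cannot be concluded from tables that leave ethnicity unstated. Leaving out C5241002 and C5241004, a viral-challenge study and a drug-interaction study, is a choice and not an inconsistency. For Day 1, C5241005 is a reasonable thing to name, since Table 3 gives it a fasted 200 mg condition. The low cost of rewording does not by itself make a case for it, because no result would differ.

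**Conclusion.** No change to the plan follows. The defect is clerical and sits in the rationale: 1 of the 3 named studies is single-dose. In C5241001, 200 mg is absent from all 7 Part A levels and all 3 Part B levels, though 16 participants are listed for Part C at that dose. Dose, sampling, endpoints and the descriptive summaries stay as they are under either reading of Sections 4.2 and 4.3.

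The slip is also unlikely to spread. Anyone who later sets these results beside earlier studies must take the values from those study reports. There the regimen and population are on record, and a single-dose dataset has no Day 5 values to take. The fasted Day 1 dose also keeps its own role, since single-dose PK is a primary objective and the breakfast comparison does not depend on other studies.

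This rests on three assumptions: that the redacted exploratory objective is not an ethnic comparison; that C5241006 included 200 mg, as Section 4.3 says; and that any comparison across studies is made outside this SAP, from the source reports.

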4.2.1. Choice of Contraception/Barrier Requirements

Human reproductive safety data are limited for sisunatovir, but there is no suspicion of human teratogenicity based on the intended pharmacology of the compound. Therefore, the use of a highly effective method of contraception is required (see [Appendix 4](#)).

PFIZER CONFIDENTIAL

CT02-GSOP Clinical Pharmacology Protocol Template (14 April 2023)

Page 27

4.3. Justification for Dose

The study dose and duration were selected based on the safety, tolerability and PK results in previous studies and the proposed clinical dose for future studies. The dose level of 200 mg BID is current proposed dose level for the following clinical development in adults. This dose was also studied in healthy participant studies C5241001, C5241005 and C5241006, which would allow the comparison of safety and PK among Westerner, Japanese and Chinese.

The single dose up to 525 mg for sisunatovir and multiple doses up to 350 mg BID × 5 days for a total dose of 9 doses were studied in Phase 1 study (C5241001), while a higher dose of 400 mg BID × 5 days was studied in C5241006. Up to a single dose of 525 mg or multiple doses of 400 mg BID, sisunatovir was generally safe and well-tolerated in all healthy participants.

The effect of food on the PK of sisunatovir has been variable in Phase 1 studies. However, the effect of food on the PK of sisunatovir using the formulation to be used in this study (dry powder blend in capsules) showed minimal food effect. Therefore, the concern of unacceptable safety and tolerability due to potentially higher exposure caused by food effect is not expected in Chinese healthy participants with administration of repeated twice daily doses (Q12 hours) of sisunatovir.

4.4. End of Study Definition

The end of the study is defined as the date of the last visit of the last participant in the study.

A participant is considered to have completed the study if they have completed all visits of the study, including the last scheduled procedure shown in the [SoA](#). Follow-up visits in addition to those in the [SoA](#) may be scheduled at investigator discretion, including to monitor open AE, or based on emerging data.

5. STUDY POPULATION

This study can fulfill its objectives only if appropriate participants are enrolled, including participants across diverse and representative racial and ethnic backgrounds. If a prescreening tool is utilized for study recruitment purposes, it will include collection of information that reflects the enrollment of a diverse participant population including, where permitted under local regulations, age, sex, race, and ethnicity. The following eligibility criteria are designed to select participants for whom participation in the study is considered appropriate. All relevant medical and nonmedical conditions should be taken into consideration when deciding whether a particular participant is suitable for this protocol.

Prospective approval of protocol deviations to recruitment and enrollment criteria, also known as protocol waivers or exemptions, is not permitted.

